1.1 Synopsis

This pilot study will evaluate a 8 to 15 day exposure to duvelisib in patients with relapsed/refractory Diffuse Large B Cell Lymphoma (DLBCL) or follicular lymphoma prior to undergoing apheresis of a mononuclear cell product for the purpose of CAR-T manufacturing. The primary objective of the study is to determine whether the immune profile of T cells can be favorably changed by short-term exposure to duvelisib prior to collection of mononuclear cells for CAR-T 19 cell manufacturing. Secondary objectives include feasibility of adherence to duvelisib for 8 to 15 day, assessment of manufacturing time of patients, assessment of proportions of CD27/CD28 T cells and CD4/CD8 double negative Gamma Delta T cells to historical controls, comparison of rates cytokine release syndrome (CRS)neurotoxicity or ICU transfer and overall response rate (ORR) at 90 days. The study will also determine if a 8 to 15 day exposure to duvelisib is safe and well tolerated in this setting.

Title:	Duvelisib Exposure to Enhance Immune Profiles of T Cells in Patients with Diffuse Large B Cell Lymphoma (DEEP T CELLS)
Study Description:	
This Pilot study will evaluate whether an 8 to 15 day exposure to Duvelisib will favorably change the immune profile of T cells prior to CAR-T 19 cell manufacturing. We hypothesize that short term exposure to Duvelisib will:
 
increase frequencies of CD27/28 double positive naïve and memory T cells.increase frequencies of CD8+CD45RO-CD27+ T cells.increase frequencies of CD4/CD8 double negative Gamma Delta T cells.
Objectives:	
Primary Objective:
 
To assess changes in T cell phenotype after 8 to 15 day exposure to duvelisib prior to collection of mononuclear cells for CAR-T cell manufacturing. 
Secondary Objectives:
 
To evaluate compliance with duvelisibTo evaluate the CAR-T 19 manufacturing timeTo describe frequencies of CD27/28 double positive T cells and CD4/8 double negative T cellsTo evaluate expansion and persistence of CAR-T cellsTo evaluate overall response rates following CAR-T cell therapyTo evaluate survival rates following CAR-T cell therapyTo describe the frequency of CRS and neurotoxicity requiring ICU transfer (for CRS or neurotoxicity) and/or treatmentDescribe the safety and tolerability profile of duvelisib

Protocol Title: Duvelisib Exposure to Enhance Immune Profiles of T Cells in Patients with Diffuse Large B Cell Lymphoma (DEEP T CELLS)

Endpoints:	
Primary Endpoint:
 
• The fold increase in the proportion of T cell phenotypes expressing CD 27/28 (to overall T cell count) after 8 to 15 day exposure to duvelisib 
Secondary Endpoints:
 
• The proportion of duvelisib consumed as evaluated by the patient pill diaries.• Manufacturing time of CAR-T 19 cells in weeks (includes manufacturing failure)• The proportion of CD27/28 double positive T cells and CD4/8 double negative T cells• CAR-T kinetics assessment by PCR• Overall response at 90 days after CAR-T cell infusion defined by the Tumor Response Assessment that are complete responders (CR) and partial responders (PR).• Progression-free Survival (PFS) at 90 days per RECIST 1.1 and Overall Survival at 90 days• ICU transfer due to CRS and/or neurotoxicity or due to the treatment with tocilizumab and/or corticosteroids• Grade III-V toxicities (as defined by CTCAE version 5.0)
Study Population:	20 patients will be enrolled with relapsed/refractory DLBCL or relapsed/refractory follicular lymphoma
Phase:	Pilot
Description of Sites/Facilities Enrolling Participants:	This study will be at Winship Cancer Institute, Emory University.
Description of Study Intervention:	Duvelisib is an oral PI3K inhibitor that is given at a dose of 25mg BID prior to manufacturing of CAR-T cells.
Study Duration:	We estimate that the duration of the study will be approximately 18 months.

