10.2 Duration of follow-up

Patients will be followed for approximately 90 days after infusion of tisagenlecleucel product. Patient records may be reviewed until death to assess progression and survival. Survival information may be collected by clinic visit, email, or telephone after ending protocol treatment and until the study is terminated, the patient dies, or the patient is lost to follow-up.

A patient will be considered lost to follow-up if he/she fails to return for three scheduled visits and is unable to be contacted by the study site staff after three attempts at contact by phone.

The following actions must be taken if a patient fails to return to the clinic for a required study visit:
The site will attempt to contact the patient and reschedule the missed visit and counsel the participant on the importance of maintaining the assigned visit schedule and ascertain if the patient wishes to and/or should continue in the study.

Patients removed from study for unacceptable adverse event(s) will be followed until resolution or stabilization of the adverse event.

- Immunogenicity samples will be taken as per schedule of events

Protocol Title: Duvelisib Exposure to Enhance Immune Profiles of T Cells in Patients with Diffuse Large B Cell Lymphoma (DEEP T CELLS)

Patients who have not initiated a new antineoplastic regimen will have the following assessments:

- Radiologic tumor assessments at 90 days
- In case of a clinically significant AE, patient will be followed for safety until resolution or permanent sequelae of all toxicities attributable to study drug(s). If the patient discontinues study drug for a clinically significant AE, the patient will be followed until resolution of the AE or the event is considered to be stable and/or chronic.

11. Inclusion and Exclusion Criteria

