- Patients with history of chronic liver disease or veno-occlusive disease
- Patients that are unable to receive prophylactic treatment for pneumocystis, herpes simplex virus (HSV), or herpes zoster (“VZV) at screening
- Patients with history of tuberculosis treatment within the 2 years prior to randomization
- Patients with prior surgery or gastrointestinal dysfunction that may affect drug absorption (e.g., gastric bypass surgery, gastrectomy). Subjects with clinically significant medical condition of malabsorption, inflammatory bowel disease, chronic conditions which manifest with diarrhea, refractory nausea, vomiting or any other condition that will interfere significantly with drug absorption.
- Concurrent administration of medications or foods that are strong inhibitors or inducers of cytochrome P450 3A (CYP3A). No prior use within 2 weeks before the start of study intervention
- Administration of a live or live attenuated vaccine within 6 weeks of randomization

12. Local Number of Participants

We will be recruiting 20 patients at Winship. We are expecting to have to enroll (consent) 30 patients to reach our recruitment goal of 20.. Patients will be registered after signing of the informed consent document and meeting all entry requirements.

13. Recruitment Methods

Investigators, nurses (CRNs), research coordinators (CRCs) and/or data managers review lists of patients who have DLBCL or relapsed/refractory follicular lymphoma and will determine if there are patients who might be eligible for the clinical trial. The CRN/CRC/data manager reviews accessible medical records to screen further for eligibility. The CRN/CRC reviews the eligibility with the physician.

Patients will be identified by their treating physicians. Clinical care team at Winship will inform potential patients about the known benefits and potential risks of a clinical trial as well as other available treatment options.

Protocol Title: Duvelisib Exposure to Enhance Immune Profiles of T Cells in Patients with Diffuse Large B Cell Lymphoma (DEEP T CELLS)

Some of the patients recruited for this protocol will be patients being treated at Emory and under the care of one or more of the study investigators. Some potential patients will be identified by their community treating physician and referred to Emory for possible participation in the clinical trial.

No incentives are provided to patients for trial participation.

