17.5.2 Analysis of Primary Endpoints

All patients that complete >75% of planned duvelisib doses and undergo leukapheresis within 2 weeks of duvelisib treatment completion will be included in the final analysis of the primary endpoint. The primary endpoint of the study to estimate the fold-change increase in CD27/CD28 double positive T cells following *in vivo* exposure to duvelisib from baseline to day 15. Our in vitro studies have shown that culturing DLBCL patients' T cells with 14 days of duvelisib increased the amount of CD27/CD28 double positive T cells from 12.2% to 32.7% (Petersen, et al, supplemental data). However, there are currently no *in vivo* background data to benchmark the expected fold-change CD27/CD28 double positive T cells over a 14-day window. Therefore, with 20 patients, this pilot study will be based on estimation on the fold change increase only and will not include a formal evaluation of the change against a null unpromising fold-change. However, we will consider this study promising if there is at least a two-fold increase in CD27+/CD28+ in at least 75% of patients.

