17.5.3 Analysis of Secondary Endpoints

- 1). Descriptive statistics will be used to calculate the proportion of patients that completed at least 75% of duvelisib doses as documented by the patient pill diaries. The proportion along with an exact 95% confidence interval will be reported.
- 2). Descriptive statistics will be used to calculate the median manufacturing time from the 10 patients that completed at least 75% of duvelisib doses. The median will be reported along with the minimum and maximum manufacturing times.
- 3). A Wilcoxon signed-rank test will evaluate the change in proportion of CD27+/CD28+ and CD4-/CD8- T cells at baseline and at day 15
- 4). Descriptive statistics will be used to calculate the *in vivo* expansion and persistence of CAR-T 19 cells post infusion as measured by serial CAR-T 19 PCR measurements.
- 5). The ORR (complete response or partial response) will be summarized along with an exact 95% confidence interval. Disease response will be based on the RECIST criteria (version 1.1). Please see section 8.2 on the definitions of disease response.

6). The 90 day PFS and OS will be estimated using the Kaplan-Meier method and calculated with corresponding 95% confidence intervals. Please see section 8.3 on the definitions of progressive disease.

7). Descriptive statistics will be used to calculate the frequency of ICU transfers due to CRS and/or neurotoxicity. Descriptive statistics will also be used to calculate the frequency of administration of tocilizumab and/or corticosteroids use for CRS and/or neurotoxicity.

8). Descriptive statistics will be used to assess the frequency of all grade toxicities as defined by CTCAE (version 5.0).

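### The 90-day overall survival interval has no named method, and the usual Kaplan-Meier interval collapses to 100–100% (or is undefined) if none of about 20 patients dies

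*Combined protocol and SAP*

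**What the plan says.** The synopsis and section 2 give the endpoint as "Progression-free Survival (PFS) at 90 days per RECIST 1.1 and Overall Survival at 90 days". The governing analysis text is section 17.5.3 item 6: "The 90 day PFS and OS will be estimated using the Kaplan-Meier method and calculated with corresponding 95% confidence intervals". It names no variance estimator, no scale for the interval and no rule for an outcome with no events.

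Two other proportions in section 17.5.3 are handled differently. For adherence (item 1), "The proportion along with an exact 95% confidence interval will be reported". For response (item 5), "The ORR (complete response or partial response) will be summarized along with an exact 95% confidence interval".

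On size, section 12 says "We will be recruiting 20 patients at Winship", with about 30 consented to reach that number, and section 17.5.2 says that "with 20 patients, this pilot study will be based on estimation on the fold change increase only". On follow-up, section 10.2 says "Patients will be followed for approximately 90 days after infusion of tisagenlecleucel product", and adds that records may be reviewed and survival information collected after that. The documents state no expected 90-day survival, no expected number of deaths and no analysis set for item 6.

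**The concern.** The endpoint is survival at a fixed time, and planned follow-up reaches that time. If nobody is censored before Day 90, the Kaplan-Meier estimate is simply the proportion alive. The interval that software normally attaches to it uses Greenwood's variance, which is zero when nobody dies. The report could then read 100% with an interval of 100% to 100%, or show no interval at all.

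In an estimation-only study, the interval is what tells a reader how little about 20 patients can show. Section 18.4 raises the possibility that the cell product made after duvelisib has a higher toxicity risk, so a survival figure that looks certain would mislead on a question the protocol itself raises. If the method is left open, it may also end up being chosen after the degenerate output has been seen.

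**Working it through.** **Plan's own figure.** There is none to reproduce: the plan states no survival rate or interval width.

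**Inputs**
- n = 20 (sections 1.1, 12 and 17.5.2). The number infused may differ, so n = 30, the number expected to be consented (section 12), is a sensitivity case.
- Nominal level 95%, taken as two-sided (section 17.5.3 item 6); z = 1.96.
- No censoring before Day 90: assumption.
- True 90-day survival S: not in the documents, so shown over a range. The only overall survival figure is a median of 6.2 months in section 3, for patients relapsing after transplant. Under an exponential curve it gives S = exp(−ln 2 × 2.96/6.2) = 0.72.

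**Formulas.** With d deaths, the estimate is Ŝ = (n − d)/n and Greenwood's variance is Ŝ(1 − Ŝ)/n. Writing se for its square root:
- plain: Ŝ ± 1.96 se, cut at 100%
- log: Ŝ × exp(± 1.96 se/Ŝ), cut at 100%
- log-log: Ŝ raised to the power exp(± 1.96 se/(Ŝ |ln Ŝ|))
- exact: Clopper-Pearson

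For d = 1: Ŝ = 0.95, se = √(0.95 × 0.05/20) = 0.0487, and the plain lower limit is 0.95 − 1.96 × 0.0487 = 0.854. For d = 0, se = 0. The exact lower limit is then 0.025^(1/20) = 0.832.

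**Intervals, n = 20 (%)**

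| Deaths | Plain | Log | Log-log | Exact |
|---|---|---|---|---|
| 0 | 100–100 | 100–100 | undefined or 100–100 | 83.2–100 |
| 1 | 85.4–100 | 85.9–100 | 69.5–99.3 | 75.1–99.9 |
| 2 | 76.9–100 | 77.8–100 | 65.6–97.4 | 68.3–98.8 |

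**Coverage, n = 20 (%).** For each S, the binomial probabilities of all d whose interval contains S were added. Zero deaths was counted as the interval 100–100%, hence as a miss. P(no deaths) = S^20.

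| True S | P(no deaths) | Plain | Log | Log-log | Exact |
|---|---|---|---|---|---|
| 72 | 0.1 | 92 | 95 | 97 | 98 |
| 80 | 1 | 92 | 93 | 96 | 98 |
| 85 | 4 | 82 | 82 | 94 | 98 |
| 90 | 12 | 88 | 88 | 84 | 99 |
| 95 | 36 | 64 | 64 | 57 | 98 |

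At the other values checked below 80% (60, 70 and 75%), coverage of the three Greenwood forms lies between 89% and 96%. At n = 30 and S = 95%, it is 78/78/72% (plain/log/log-log), with P(no deaths) = 21%.

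**Where the loss comes from.** Given at least one death at n = 20, plain/log/log-log coverage is 99.7/99.7/95% at S = 90% and 99.6/99.9/88% at S = 95%. The zero-death outcome therefore accounts for most of the shortfall at these values. At S = 85%, plain and log also miss with one death, because their lower limits (85.4% and 85.9%) exceed 85%.

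**Log-log with an exact lower limit at zero deaths.** At S = 85, 90 and 95% the limit of 83.2% turns the zero-death miss into a hit, so P(no deaths) is added back. At 95%: 56.6 + 35.8 = 92.5%. Coverage at 72/80/85/90/95% becomes 97/96/98/96/92%.

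**The case against.** The strongest reply is that the plan does not choose a failing interval. Item 6 names neither Greenwood nor a scale, and an interval that behaves well at zero events would satisfy its wording. That stands: the fault is an unspecified method whose usual default fails.

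Several limits also stand. High 90-day survival is an assumption; at the 72% implied by the only survival figure in the documents, coverage is 92–97%. That figure does describe a different group, and sections 4.1.4 and 11.1 select patients before entry and before infusion, so values above it cannot be excluded. Counting zero deaths as a miss is partly a convention on the log-log scale, where the interval is undefined; a blank interval is still no answer. Deaths are recorded separately and the committee reviews safety, so a reader would also see the raw count.

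Three stronger readings are tempting, and the documents do not support them:
- That no choice of scale helps. Log-log alone does not help at zero deaths, but with an exact limit there it largely repairs the problem. With one death its lower limit (69.5%) is below the exact one (75.1%), so it is not over-optimistic.
- That Kaplan-Meier is the wrong estimator and a simple proportion should replace it. The plan allows withdrawal and loss to follow-up, and the Day 90 visit has a ±3-day window, so some patients may be censored before Day 90. A simple proportion does not handle that.
- That progression-free survival is equally harmed. With more events it is little affected.

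**Conclusion.** The point holds as a gap in specification for 90-day overall survival. If nobody dies, the usual interval reads 100–100% or is undefined, where 20 of 20 alive is compatible with true survival as low as 83%. With one or two deaths, the plain and log lower limits lie about 9 to 11 points above the exact ones.

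How often this matters depends on a true survival rate that the documents do not give. Coverage falls to 84–88% at 90% and 57–64% at 95%. At 80% or lower, the chance of no deaths is about 1% or less, and coverage is 92–97% at 72% and 80%, with 89% the lowest value found from 60% to 80%. These figures assume n = 20 and complete follow-up to Day 90; the shortfall at 95% persists at n = 30. The consequence is false precision in a descriptive secondary result. The only criterion for calling the study promising concerns CD27/CD28, and it is untouched.

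**What to change.** In section 17.5.3 item 6, keep the Kaplan-Meier estimate and add one sentence naming the 95% interval for 90-day overall survival, and for progression-free survival for consistency. Either of these would serve:
- the beta product confidence procedure, which allows censoring, is valid at zero events and equals Clopper-Pearson when nobody is censored before Day 90 (the preferable choice, since it matches items 1 and 5 in that case); or
- the log-log Greenwood interval, with an exact lower limit when there are no deaths.

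The same sentence should state the analysis set and the time origin, which item 6 leaves open. The cost is that wording and, compared with a plain or log interval, a somewhat wider result: with one death in 20, 75.1–99.9% in place of 85.4–100%. No patients, visits or data are added.

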1.2 Schema

Days -14 to 0	Screening
	
• Total n= 20• Obtain informed consent• Screen potential participants by inclusion and exclusion criteria• Obtain history, document
Day 1	Follow-up assessments of study endpoints and safety Baseline assessments/ Study Intervention
	
• Administer initial dose of Duvelisib
	Refer to Section 1.3, Schedule of Activities
Day 8	
	
• Refer to Section 1.3, Schedule of Activities
Day 15	
	
• Refer to Section 1.3, Schedule of Activities
CART-T Day 0-90	Post CAR-T 19 Infusion Assessments
	
• Refer to Section 1.3, Schedule of Activities

1.3 Schedule of Assessments

Table 1: Pre and During Study Assessments on duvelisib (Day 1= First day of duvelisib)

Procedures and Tests	Days -14 to 0	Day 8 +/-1	Day 15 +/-2
Medical History	X		
Physical Exam	X	X	X
Performance Status	X	X	X
Vital Signs	X	X	X
Labs: [*]	X	X	X
CBC	X	X	X
CMP	X	X	X
TSH	X		
Magnesium	X		
Phosphorous	X	X	X
HIV Ag/Ab	X		
Hepatitis Serologies	X		
Covid-19 PCR (-7 to 0)	X		
EKG	X		
Immunophenotyping of T-Cells	X		X
PET/CT [*]	X		
Serum or Urine Pregnancy Test ^{**}	X		
Adverse Events		X	X

* Standard-of-care

** Standard-of-care. Also see section 11.1 regarding risk to fetus and requirement for contraception while on study

Table 2: Post CAR-T 19 Cell Infusion Assessments (post-hospital discharge, will be captured with chart review) (CAR-T Day 0 (cD0)= Date of CAR-T infusion)

Procedures and Tests	Day 7 +/-1 (post CAR-T)	Day 14 +/-2 (post CAR-T)	Day 28 +/-2 (post CAR-T)	Day 42 +/-3 (post CAR-T)	Day 90 +/-3 (post CAR-T)
CAR-T 19 PCR [*]	X	X	X	X	X
Immunophenotype of CAR-T [*]	X	X	X	X	X
PET/CT or CT [*]					X

* Standard-of-care

2. Objectives (and Endpoints)

OBJECTIVES	ENDPOINTS
Primary	
1. To assess the increase in CD27+/CD28+ T cells, after 8 to 15 day exposure duvelisib prior to collection of mononuclear cells for CAR-T cell manufacturing.	1. The fold change increase in proportion of T cell phenotypes co-expressing CD27/28 using multiparametric flow cytometry.
Secondary	
1. To evaluate patient compliance with duvelisib. 2. To evaluate the time required for manufacturing CAR-T using mononuclear cells from duvelisib-treated patients. 3. To describe the frequencies of CD27/28 double positive T cells and CD4/8 double negative T cells 4. To evaluate expansion and persistence of CAR-T cells 5. To evaluate overall response rates following CAR-T cell therapy 6. To evaluate survival rates following CAR-T cell therapy 7. To describe the frequency of CRS and neurotoxicity requiring ICU transfer (for CRS or neurotoxicity) and/or treatment 8. Describe the safety and tolerability profile of duvelisib	1. The proportion of duvelisib consumed as documented by the patient on the pill diaries. 2. Manufacturing time of CAR-T 19 cells in weeks (includes manufacturing failure) 3. The proportion of CD27/28 double positive T cells and CD4/8 double negative T cells 4. CAR-T kinetics assessment by PCR 5. Overall response (per iRECIST) at 90 days after CAR-T cell infusion defined by the Tumor Response Assessment that are complete responders (CR) and partial responders (PR). 6. Progression-free Survival (PFS) at 90 days per RECIST 1.1 and Overall Survival at 90 days 7. ICU transfer due to CRS and/or neurotoxicity or due to the treatment with tocilizumab and/or corticosteroids 8. Grade III-V toxicities (as defined by CTCAE version)

3. Background

Diffuse Large B Cell Lymphoma (DLBCL) and relapsed/refractory follicular lymphoma:

Lymphoma is a group of blood cell tumors that arise from the lymphatic systems and can be separated into two categories: Non-Hodgkin Lymphoma (NHL) and Hodgkin Lymphoma (HL). NHL accounts for about 4% of all cancers with an estimated 74,000 new cases diagnosed in 2018.¹ There will be an estimated 20,000 deaths from NHL, which accounts for 3% of all cancer deaths. Diffuse large B cell lymphoma (DLBCL) and follicular lymphoma (FL) are the most common NHL, accounting for nearly 65% of cases.² Standard treatment for DLBCL is a rituximab based regimen in combination with cyclophosphamide, doxorubicin, vincristine, etoposide and prednisone (R-CHOP or R-EPOCH).³ The five year overall survival (OS) for DLBCL is 62% in the United States and for localized DLBCL, the OS is even more impressive at over 80%.^{4,5} Despite the favorable outcomes with DLBCL, one third of patients will have relapsed or refractory disease.² These patients are treated with salvage chemotherapy and consolidation treatment with autologous stem cell transplant (ASCT). Unfortunately, about 50% of those patients that receive ASCT will ultimately relapse, and further treatment options become severely limited with a median OS of 6.2 months.⁴

Recently, a novel immunotherapy that manufactures T cells to express the chimeric antigen receptor (CAR-T cells) against CD19, that is pan-expressed on B cells, has been shown to have high response rates in relapsed/refractory B cell cancers including those that have previously received an ASCT.⁶ CAR-T cells provide a promising new treatment for heavily pre-treated patients with B cell malignancies, however, there are a sub-group of patients who are unable to manufacture a sufficient amount of CAR-T cells, have poor expansion of CAR-T cells in vivo, or lose persistence of their CAR-T cells post infusion. Thus, better manufacturing of T cells to make them more potent with longer duration are critical to enhancing the success of CAR-T cells.

Chimeric Antigen Receptor T (CAR-T) Cells:

Chimeric antigen receptor (CAR) T cells are genetically engineered T cells that recognize specific tumor antigens.⁷ The genes encoding for the CAR are inserted into the T cells using a viral vector with RNA genetic material that is then reverse transcribed into the T cells DNA.⁸ The CAR is then transcribed and translated and then expressed on the cell surface where it is able to recognize tumor antigens. There are two components of the CAR including the antigen-recognition domain and the T cell signaling domain. In earlier generations of CARs, the T cell signaling domain only contained an intracellular activation domain. Newer generations have added a single co-stimulatory domain (CD28 or 4-1BB) or two co-stimulatory domains (See Figure 1). For B cell malignancies, including acute lymphoblastic leukemia (ALL) and DLBCL, the most common antigen used for CAR-T cells manufacturing is CD19. CD19 is pan-expressed on B cells and cannot be downregulated on normal B cells. Numerous single center and multi-center studies have been published about CD19 CAR-T cells against NHL and has shown an overall response rate (ORR) ranging from 71%-100%.⁷

Remissions of hematologic malignancy with CAR T cell therapy are associated with one of two profiles of CAR T cell expansion kinetics. Some trials positively associate the ratio of peak CAR T to tumor cells with remission, whereas the bulk of trials associate long-term persistence of CAR T with continued remission. In support of the latter mechanism, expansion and persistence of a single clone (defined by CAR insertion site) comprising 94% of the total CAR T cells was sufficient to induce remission. In study of 41 patients who received CAR T cell therapy to treat CLL, Fraietta et al associated the frequency of CD8+CD27+CD45RO- T cells prior to CAR T manufacture with

remission.⁹ These clinical observations suggest CAR T cell phenotype, such as expression of CD27 and CD28, influences response to therapy.

Figure 1: Chimeric antigen receptor (CAR) structures.

[figure not shown]

Figure 1: Structure of CAR-T cells (Brudno & Kochenderfer)

Phosphoinositide 3-Kinase (PI3K)

PI3K proteins are divided into three classes of which only Class IA PI3K molecules have been implicated in human cancers, prompting development of isoform-selective inhibitors to Class IA PI3K.¹⁰ Analysis of evolutionary conservation across known class I PI3K signaling cascades reveals the greatest conservation in signaling along the insulin/IGF-1/AKT pathway, suggesting PI3K primarily evolved to regulate cellular proliferation and metabolic changes in response to glucose.¹¹

PI3Ks are involved in the generation of lipid second messengers and contain eight catalytic subunits of PI3K, with the P110 gamma and the P110 delta subunits being expressed at much higher levels in immune cells.^{12,13} The PI3K p110 subunits work by phosphorylating phosphatidylinositol 4,5 bisphosphate (PIP2) into phosphatidylinositol 3, 4,5 triphosphate (PIP3), which enables anchorage and association of cytosolic proteins near the lipid bilayer, enabling complex signal transduction cascades to occur.¹⁰ In the case of T cells, metabolism of glucose is closely linked to the replicative capacity of the cells, with T cells capable of oxidative phosphorylation exhibiting enhanced replicative capacity whereas T cells that rely upon glycolysis exhibit reduced replicative potential, as reviewed by Van der Windt et al 2013.¹⁴

PIP3 then goes on to function as a second messenger that initiates multiple signaling cascades, including the phosphorylation of AKT, a serine/threonine protein kinase, leading to downstream

survival and differentiation signals such as mechanistic target of rapamycin 1 (mTOR).^{15,16} mTOR, also a serine/threonine kinase, is regulated by amino acids and glucose levels. Upon T cell activation, there is an increase in uptake of amino acids and glucose leading to activation of mTOR1 and this activation is required to maintain the T cell effector functions.¹⁷⁻²⁰ Activation of mTOR1 also promotes induction of aerobic glycolysis, as well as assistance in maintaining it, which leads to increased differentiation and effector functions, which are shown to be less efficacious in terms of adoptive T cell therapies.²⁰ By inhibiting mTOR through inhibition of PI3K. PI3K inhibitors promotes memory T cell phenotype by inhibiting aerobic glycolysis and preventing terminal differentiation.²⁰ One PI3K inhibitor, Idelalisib, inhibits only the delta catalytic subunit, which blocks lymphocyte function.¹¹ Duvelisib, another PI3K inhibitor, demonstrates inhibition of both PI3K-delta and gamma, but is much more selective for the delta than the gamma isoform of PI3K.^{15,15} Indeed, using whole blood assays, duvelisib achieves inhibition of PI3K delta and gamma at clinically feasible doses (Pachter and Weaver, SITC 2008), which may be important for modulating ratios of CD8:CD4 T cells (Funk et al., SITC 2019; unpublished data, [name] Lab). By targeting either PI3K delta alone or both PI3K delta and gamma catalytic subunits, that are predominantly expressed on immune cells, PI3K inhibitors lead to partial blockade of terminal differentiation of T cells.

T cells and Cancer Immunotherapy

T cells can be categorized based upon whether their T cell receptor (TCR) recognizes antigen by major histocompatibility complex (MHC) in an independent or dependent manner. Alpha Beta T cells contain a TCR that recognize peptide presented by class I or II MHC, whereas Gamma Delta T cells recognize antigens independent of MHC. Gamma Delta T cells are a small and unique population of T cells that comprise less than 5% of the total T cell population.²¹ They generally do not express CD4 or CD8 and have the unique role of serving as both effector T cells and initiating and maintaining adaptive immune responses.²² Gamma-Delta T cells are able to secrete cytokines, including IL-4 and TNFa, that can directly attack and kill tumor cells. They can also act as antigen presenting cells (APCs) and have the capacity to induce CD4+ and CD8+ antigen specific T cells.²³ Pre-clinical studies have shown that gamma delta CAR-T cells have a more naïve T cell phenotype and that their cytotoxicity was equivalent to alpha beta CAR-T cells.²⁴

Alpha Beta(+) TCR T cells are the predominant T cells comprising >95% of T cells and can be further sub-categorized into helper, cytotoxic, memory or regulatory T cells.²³ Naïve T cells are antigen inexperienced and are characterized by the expression of CD45RA, CD62L and the co-stimulatory molecules CD27 and CD28. Central memory T cells, which have previously encountered an antigen, express CD45RO, CD27 and CD62L and thus, retain their proliferative capacity. Effector memory T cells lack CD27 and CD62L which reduces their proliferative capacity.²⁵

One unintended consequence of cytotoxic chemotherapy, is depletion of healthy T cells, including naïve and central memory T cell subsets, that have the most potent ability to respond to malignant antigens, have greater expansion potential and greater anti-cancer activity.²⁶⁻²⁷ Numerous studies have shown superior persistence and anti-tumor activity with minimally differentiated T cells, including naïve, stem cell and central memory T cells.²⁸⁻³⁰

These observations also apply to CAR T cells, as study of determinant of outcomes revealed that frequencies of memory and naïve cells prior to CAR T manufacture appear to be associated with remissions.³¹

